**Table 7.8: Management of Hepatocellular Toxicity Associated with Cabozantinib**

Event – Elevation of ALT, AST, or Total Bilirubin (CTCAE v4)	Management
Grade 1  ALT or AST > ULN – 3.0 x ULN Bilirubin > ULN – 1.5 x ULN	
 
• Dose adjustment is usually not required.
 
• Consider discontinuing concomitant hepatotoxic medications and add supportive care as indicated.
 

Grade 2 a,b  ALT or AST > 3.0 – 5.0 x ULN Bilirubin > 1.5 – 3.0 x ULN	
 
• Interrupt cabozantinib if lasting longer than 1 week and consider more frequent monitoring of ALT, AST, and bilirubin.
 
• Restart cabozantinib after lab abnormalities have resolved to at least CTCAE Grade ≤ 1 or baseline.
 

Grade 3 a,b  ALT or AST > 5.0 – 20.0 x ULN Bilirubin > 3.0 – 10.0 x ULN	
 
• Interrupt cabozantinib and consider more frequent monitoring of ALT, AST, and bilirubin.
 
• Restart cabozantinib at a reduced dose after lab abnormalities have resolved to at least CTCAE Grade ≤ 1 or baseline.
 
• Discontinue if lab abnormalities cannot be reversed despite interruption of study treatment.
 

Grade 4 b  ALT or AST > 20.0 x ULN Bilirubin > 10 x ULN	
Subjects should have cabozantinib interrupted immediately. Discontinue cabozantinib unless the following criteria are met:
 
 
• Subject is deriving clear clinical benefit as determined by the Investigator, and approved by the Principal Investigator.
 
• Toxicity can be managed with a dose reduction following recovery to Grade 1 (or baseline) and optimal medical care.
 

a Elevations of aminotransferases when hepatic metastases are present may not require dose modifications if there is less than a doubling in the aminotransferases from baseline and if there are no progressive elevations in serum bilirubin concentration or coagulation factors.	

#### **7.9.14 Infections and Infestations**

Infections are commonly observed in cancer subjects. Predisposing risk factor include a decreased immune status (*e.g.* after myelosuppressive anticancer therapies, splenectomy), destructive growth of the underlying malignancy including bone marrow infiltration with suppression of normal hematopoiesis, as well as the presence of IV devices.

Infections and abscesses should be treated with appropriate local care and systemic therapy. Cabozantinib should be interrupted until adequate healing has taken place.

#### **7.9.15 Blood and Lymphatic System Disorders**

Hematological toxicities (*ie*, neutropenia and thrombocytopenia) and associated complications have been observed after administration of cabozantinib and may be managed with dose interruptions and/or dose reductions. Subjects with hematologic toxicities may require additional or more frequent laboratory tests according to institutional guidelines.

Dose reductions or dose interruptions for hematological toxicities are not mandated but can be applied as clinically indicated. Supportive care for thrombocytopenia or anemia, such as transfusions, may be managed according to institutional guidelines. The use of colony-stimulating

growth factors should be considered. Febrile neutropenia or evidence of infection associated with neutropenia must be assessed immediately and treated appropriately and in a timely manner according to institutional guidelines.

#### **7.9.16 Fatigue**

Common causes of fatigue, such as anemia, deconditioning, emotional distress (depression and/or anxiety), poor nutrition, dehydration, sleep disturbance, and hypothyroidism should be ruled out and treated according to standard of care. Pharmacological management should be considered after disease-specific morbidities have been excluded when not prohibited.

#### **7.9.17 Weight Loss**

Anorexia and weight loss should be managed according to local standard of care including nutritional support. Pharmacologic therapy should be considered for appetite enhancement when not prohibited by a particular protocol.

#### **7.9.18 Corrected QT Prolongation**

The effect of orally administered cabozantinib 140 mg qd on QTc interval was evaluated in a placebo-controlled study in subjects with MTC. A mean increase in QTcF of 10-15 ms was observed after 4 weeks after initiating cabozantinib treatment. A concentration-QTc relationship could not be definitively established. Changes in cardiac wave form morphology or new rhythms were not observed. No cabozantinib-treated subjects in this study had a QTcF > 500 ms. Review of the larger safety database (~5000 subjects exposed to cabozantinib in clinical trials and in post-marketing experience) confirmed the absence of safety concerns associated with QT prolongation. There were no events of torsades de pointes reported.

Concomitant treatment with strong cytochrome P450 (CYP) 3A4 inhibitors, which may increase cabozantinib plasma concentrations, should be avoided.

If at any time on study there is an increase in QTcF to an absolute value > 500 ms, two additional ECGs must be performed with intervals not less than 3 min apart within 30 min after the initial ECG. If the average QTcF from the three ECGs is > 500 ms, the following actions must be taken:

- Interrupt cabozantinib treatment
- Hospitalize symptomatic subjects (e.g. with palpitations, dizziness, syncope, orthostatic hypotension, a significant ventricular arrhythmia on ECG) for a thorough cardiology evaluation and management
- Consider cardiology consultation for asymptomatic subjects for evaluation and management
- Check electrolytes, especially magnesium, potassium and calcium; correct abnormalities as clinically indicated
- Check concomitant medications for any medication that may have contributed to QT prolongation, and if possible, discontinue these medications (<http://www.qtdrugs.org>)
- Repeat ECG triplicates hourly until the average QTcF is ≤ 500 msec, or otherwise determined by consultation with a cardiologist or appropriate expert.

Subjects with QTc prolongation and symptoms must be monitored closely until the QTc elevation and symptoms have resolved. Cabozantinib treatment may be restarted at a reduced dose level if all of the following conditions are met:

- Symptoms are determined to be unrelated to the QT interval prolongation
- The QTcF value > 500 ms is not confirmed

- Cabozantinib treatment has been interrupted through a minimum of 1 week following the return of the QTcF to  $\leq 500$  ms.
- QT prolongation can be unequivocally associated with an event other than cabozantinib administration and is treatable/has been resolved  
Following reinitiation of study treatment, ECGs must be repeated weekly for 2 weeks, then every 2 weeks for 1 month, then according to the protocol-defined time points.

Cabozantinib treatment must be permanently discontinued if either of the following applies:

- Cardiac evaluation confirms that symptoms are the consequence of QT interval prolongation
- Recurrence of QTcF prolongation after reinitiation of study treatment at a reduced dose

#### **7.9.19 Electrolyte Disorders**

Serum electrolyte disorders including hyponatremia, hypokalemia, hypomagnesemia, and hypophosphatemia have been reported during treatment with cabozantinib, and serum electrolyte levels should be monitored frequently while receiving cabozantinib. Clinically relevant electrolyte disorders should be managed according to the dose modification guidelines as outlined in Section 7.3 or as clinically indicated. Standard clinical practice guidelines should be used for management of electrolyte disorders and may include oral or intravenous replacement.

#### **7.9.20 Endocrine Disorders**

Treatment-emergent elevation of thyroid-stimulating hormone (TSH) has been observed with cabozantinib treatment. Currently available data are insufficient to determine the mechanism of thyroid function test alterations and its clinical relevance. Management of thyroid dysfunction (e.g. symptomatic hypothyroidism) should follow accepted clinical practice guidelines.

#### **7.9.21 Angioedema**

Angioedema should be managed according to standard practice. The subject should be observed until symptoms resolve, with particular attention to maintaining an open airway.

### **7.10 Duration of Therapy and Criteria for Removal from Study**

Subjects may discontinue study treatment or withdraw their consent to participate in the study at any time without prejudice. The investigator may withdraw a subject from study treatment or from the study if, in his or her clinical judgment, it is in the best interest of the subject or if the subject cannot comply with the protocol.

In addition, any of the following conditions require discontinuation of the subject from study treatment:

- An AE or intercurrent illness that in the opinion of the investigator warrants the subject's withdrawal from study treatment;
- The investigator believes it is not in the best interest of the subject to continue on study
- Specific conditions described in the Management of Adverse Events Section;
- Necessity for treatment with other anticancer treatment prohibited by protocol;
- Sexually active subjects who refuse to use medically accepted barrier methods of contraception (e.g., male condom, female condom) during the course of the study and for 4 months after discontinuation of study treatment;

- If the subject does not recover from his or her toxicities to tolerable Grade  $\leq 2$  within 6 weeks, the subject will have study treatment discontinued unless there is unequivocal evidence that the subject is benefitting. In this situation, a subject may be able to restart therapy with a dose reduction upon resolution of the toxicity and with agreement of the principal investigator / Sponsor;
- Request by regulatory agencies for termination of treatment of an individual subject or all subjects under the protocol;
- Significant noncompliance with the protocol schedule in the opinion of the investigator;
- Subjects who cannot tolerate the minimum protocol-specified dose of study treatment will have study treatment discontinued;
- Progressive disease (PD) or the subject no longer experiences clinical benefit as determined by the investigator

At any time, the study sponsor (Exelixis) or the sponsoring institution (Weill Cornell Medicine) can terminate this study. Should this occur, Exelixis and the investigator will arrange the procedures on an individual study basis after review and consultation. In terminating the study, Exelixis and the investigator will ensure that adequate consideration is given to the protection of the subjects' interests. Upon study termination, the investigator(s) shall cease enrolling subjects into the study, and shall discontinue conduct of the study as soon as is medically practicable.

## 8 CONCOMITANT MEDICATIONS AND THERAPIES

### 8.1 Allowed Therapy

- Individualized anticoagulation therapy with heparin or direct factor Xa inhibitors rivaroxaban, edoxaban, or apixaban is allowed if it can be provided safely and effectively under the following circumstances:
  - At the time of first dose of study treatment:
    - Low dose low molecular weight heparins (LMWH) for prophylactic use are allowed if clinically indicated and the benefit outweighs the risk per the Investigator's discretion.
    - Therapeutic doses of LMWH or the direct factor Xa inhibitors rivaroxaban, edoxaban, or apixaban are allowed if the subject has no evidence of brain metastasis, has been on a stable dose of the anticoagulant for at least 1 week, and has had no clinically significant hemorrhagic complications from the anticoagulation regimen or the tumor. See Section 7.2 for prohibited anticoagulants.
  - After first dose of study treatment:
    - Low dose low molecular weight heparins (LMWH) for prophylactic use are allowed if clinically indicated and the benefit outweighs the risk per the Investigator's discretion.
    - Therapeutic doses of LMWH or the direct factor Xa oral inhibitors rivaroxaban, edoxaban, or apixaban are allowed if clinically indicated (e.g., for the treatment of DVT), and the benefit outweighs the risk per the Investigator's discretion. See section 6.3.1.3.4 for management of thromboembolic complications while on study. See section 7.2 for prohibited anticoagulants.
  - Accepted clinical guidelines regarding appropriate management while receiving any kind of anticoagulation therapy must be followed. This includes, but is not limited to,

subject education regarding the potential adverse drug reactions, monitoring laboratory parameters, dose adjustments (e.g., due to kidney dysfunction). Caution is warranted in settings associated with an increased risk for bleeding such as gastrointestinal cancers, urothelial cancers, gastrointestinal mucosal abnormality (e.g., mucositis), renal or hepatic impairment, thrombocytopenia, arterial hypertension, or prior history of gastrointestinal bleed. For direct factor Xa inhibitors, the potential for drug-drug interaction with other concomitant medications, as well as gastrointestinal absorption, should be considered. Aspirin and other nonsteroidal anti-inflammatory drugs (NSAIDs) should not be used concomitantly with heparin or factor Xa inhibitors due to the increased risk for bleeding complications. The risks and benefits of the use of anticoagulants should be reassessed on a regular basis. For more information regarding the use of anticoagulants, refer to the prescribing information of the anticoagulant and accepted clinical practice guidelines.

- Antiemetics and antidiarrheal medications are allowed prophylactically according to standard clinical practice if clinically indicated.
- Granulocyte colony-stimulating factors (G-CSF or GM-CSF) are allowed if used per clinical guidelines (e.g. ASCO or ESMO guidelines).
- Bisphosphonates can be used to control bone loss or hypocalcemia if the benefit outweighs the risk per the investigator's discretion.
  - Note: osteonecrosis of the jaw has been reported in subjects using bisphosphonates. Oral examinations are recommended at screening to determine eligibility and periodically during the study. In addition, subjects should be advised regarding oral hygiene practice and to quickly report symptoms to the investigator. Frequent monitoring for potentially overlapping toxicities with study treatment is recommended.
- Transfusions and hormone replacement should be utilized as indicated by standard clinical practice.
- For restrictions on oral anticoagulants see Section 7.
- Potential drug interactions with cabozantinib are summarized in Section 8.3.

## 8.2 Prohibited or Restricted Therapy

The following therapies are prohibited until study treatment has been permanently discontinued:

- Any investigational agent or investigational medical device.
- Any nonprotocol systemic anticancer treatment (e.g. chemotherapy, immunotherapy, radionuclides, drugs or herbal products used specifically for the treatment of the cancer under investigation).
  - The following therapies should be avoided until study treatment has been permanently discontinued or until otherwise specified:
- Local anticancer treatment including palliative radiation, ablation, embolization, or surgery with impact on tumor lesions should not be performed until radiographic progression per RECIST 1.1 has been established.
- Erythropoietic stimulating agents (e.g. epoetin alfa and darbepoetin alfa) should not be used based on a report of increased risk of tumor recurrence/progression associated with erythropoietin (Wright et al 2007).
- Concomitant medications that are known to prolong the QTc interval should be avoided in subjects who receive cabozantinib until they have permanently discontinued cabozantinib treatment (refer to <http://www.qtdrugs.org> for a list of drugs which have the potential to prolong the QTc interval).
- Chronic co-administration of cabozantinib with strong inducers of the CYP3A4 family (e.g. phenytoin, carbamazepine, rifampin, rifabutin, rifapentine, phenobarbital, and St. John's

Wort) may significantly decrease cabozantinib concentrations and should be avoided. Selection of alternate concomitant medications with no or minimal CYP3A4 enzyme induction potential is recommended.

- Caution must be used when discontinuing treatment with a strong CYP3A4 inducer in a subject who has been concurrently receiving a stable dose of cabozantinib, as this could significantly increase the exposure to cabozantinib.
- Co-administration of cabozantinib with strong inhibitors of the CYP3A4 family (e.g. boceprevir, conivaptan, posaconazole, ketoconazole, itraconazole, clarithromycin, atazanavir, indinavir, nefazodone, nelfinavir, saquinavir, ritonavir, lopinavir, telaprevir, telithromycin, and voriconazole) may increase cabozantinib concentrations and should be avoided. Grapefruit, star fruit, and Seville oranges may also increase plasma concentrations of cabozantinib and should be avoided.
- Additional information on potential drug interactions with cabozantinib is provided in Section 8.3.

### 8.3 Potential Drug Interactions

Cytochrome P450: Data from a clinical drug interaction study (Study XL184-008) show that clinically relevant steady-state concentrations of cabozantinib appear to have no marked effect on the area under the plasma concentration-vs-time curve (AUC) of co-administered rosiglitazone, a CYP2C8 substrate. Therefore, cabozantinib is not anticipated to markedly inhibit CYP2C8 in the clinic, and by inference, is not anticipated to markedly inhibit other CYP450 isozymes that have lower [I]/Ki values compared to CYP2C8 (ie, CYP2C9, CYP2C19, CYP2D6, CYP1A2, and CYP3A4). In vitro data indicate that cabozantinib is unlikely to induce cytochrome P450 enzymes, except for possible induction of CYP1A1 at high cabozantinib concentrations (30 µM).

Cabozantinib is a CYP3A4 substrate and a weak substrate for CYP2C9 (but not a CYP2D6, CYP2C8, CYP2C19, CYP2B6, or CYP1A2 substrate), based on data from in vitro studies. Results from a clinical pharmacology study, XL184-006, showed that concurrent administration of cabozantinib with the strong CYP3A4 inducer, rifampin, resulted in an approximately 77% reduction in cabozantinib exposure (AUC values) after a single dose of cabozantinib in healthy volunteers. Chronic co-administration of cabozantinib with strong inducers of the CYP3A4 family (e.g. phenytoin, carbamazepine, rifampin, rifabutin, rifapentine, phenobarbital, and St. John's Wort) may significantly decrease cabozantinib concentrations. The chronic use of strong CYP3A4 inducers should be avoided. Other drugs that induce CYP3A4 should be used with caution because these drugs have the potential to decrease exposure (AUC) to cabozantinib. Selection of alternate concomitant medications with no or minimal CYP3A4 enzyme induction potential is recommended.

Results from a clinical pharmacology study, XL184-007, showed that concurrent administration of cabozantinib with the strong CYP3A4 inhibitor, ketoconazole, resulted in a 38% increase in the cabozantinib exposure (AUC values) after a single dose of cabozantinib in healthy volunteers. Co-administration of cabozantinib with strong inhibitors of the CYP3A4 family (e.g. boceprevir, conivaptan, posaconazole, ketoconazole, itraconazole, clarithromycin, atazanavir, indinavir, nefazodone, nelfinavir, saquinavir, ritonavir, lopinavir, telaprevir, telithromycin, and voriconazole) may increase cabozantinib concentrations. Grapefruit, star fruit and Seville oranges may also increase plasma concentrations of cabozantinib and should be avoided. Strong CYP3A4 inhibitors should be avoided and other drugs that inhibit CYP3A4 should be used with caution because these drugs have the potential to increase exposure (AUC) to cabozantinib. Selection of alternate concomitant medications with no or minimal CYP3A4 enzyme inhibition potential is recommended.

Please refer to the drug interaction tables at the following websites for lists of substrates, inducers, and inhibitors of selected CYP450 isozyme pathways:

<http://medicine.iupui.edu/clinpharm/ddis/table.aspx>

<http://www.fda.gov/Drugs/DevelopmentApprovalProcess/DevelopmentResources/DrugInteractionsLabeling/ucm080499.htm>

**Protein Binding:** Cabozantinib is highly bound (approximately 99.9%) to human plasma proteins. Therefore, highly protein bound drugs (e.g., diazepam, furosemide, dicloxacillin, and propranolol) should be used with caution with cabozantinib because there is a potential displacement interaction that could increase free concentrations of cabozantinib and/or a co-administered highly protein bound drug (and a corresponding increase in pharmacologic effect). Factors that influence plasma protein binding may affect individual tolerance to cabozantinib. A case of a drug-drug interaction between cabozantinib and warfarin that may involve displacement of plasma protein bound drug has been reported in the literature [41]. Because warfarin is a highly protein bound drug with a low therapeutic index, administration of warfarin at therapeutic doses is not allowed in subjects receiving cabozantinib due to the potential for a protein binding displacement interaction.

#### **Other Interactions:**

Food may increase exposure levels of cabozantinib by 57%, fasting recommendations should be followed. In vitro data suggest that cabozantinib is unlikely to be a substrate for P-glycoprotein, but it does appear to have the potential to inhibit the P-glycoprotein transport activity. Therefore, cabozantinib may have the potential to increase plasma concentrations of co-administered substrates of P-glycoprotein. Additional details related to these overall conclusions can be found in the investigator brochure.

Administration of the proton pump inhibitor (PPI) esomeprazole resulted in no clinically-relevant effect on cabozantinib plasma PK in healthy volunteers. Therefore, concomitant use of gastric pH modifying agents (ie, PPIs, H2 receptor antagonists, and antacids) is not contraindicated in subjects administered cabozantinib.

Additional details regarding potential drug interactions with cabozantinib can be found in the investigator brochure.

Cabozantinib was shown to be a substrate of drug transporter MRP2 in an in vitro assay. Administration of MRP2 inhibitors to subjects may result in increases in cabozantinib plasma concentrations.

## **9 CORRELATIVE/SPECIAL STUDIES**

### *i. Cell-free plasma DNA and archival tissue:*

Plasma samples for ctDNA will be collected for analysis prior to treatment (as close to biopsy timing as possible), at 12 weeks, and at progression using the PC specific platform developed in collaboration with [name]. We will also request archival paraffin embedded tissue to incorporate tissue-based and cell free DNA approaches to assess PC pathway changes and genomic /epigenomic alterations and will correlate with clinical response. We will evaluate the association of molecular biomarkers with treatment response.

We will also compare tumor tissue targeted genomic sequencing results (CLIA test used for inclusion) with ctDNA findings at baseline and determine their concordance, identify and track these alterations, monitor ctDNA tumor content and quantify relevant tumor clones on therapy, and analyze somatic

alterations that emerge at the time of progression/therapy resistance. We predict that a molecularly defined subset of CRPC will preferentially respond to Cabozatinib and this group is detectable using plasma-based assays. These data will help develop a non-invasive blood-based method for future trial inclusion criteria, as well as provide new insights into mechanisms of response/resistance to Cabozantinib in prostate cancer.

ii. *Immune Assays:*

Mandatory collection of 5 mL of plasma or serum in Serum Separation Tubes will be obtained at baseline, every 12 weeks, and at the time of disease progression. These will be aliquoted in 100 microliter fractions and stored at -80 degrees C prior to thaw for analysis.

iii. *Tumor Tissue:*

Metastatic tumor tissue biopsies will be taken with core needle or excisional biopsy. Fine needle aspiration is **not** allowed. It is encouraged that 6 core samples be collected from a single site with a minimum of 4 core samples collected. The biopsy sample will be split into two components, one formalin fixed for histological and immunohistochemical analyses, as well as possible DNA mutation analysis. The other component will be flash frozen for RNA isolation and sequencing. In addition to the typical hematoxylin and eosin staining for tumor morphology and histologic classification.

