    - i. If urine dipstick is positive, then:
      1. Urine protein/creatinine ratio (UPCR)  $\leq 1 \text{ mg/mg}$  ( $\leq 113.2 \text{ mg/mmol}$ )
11. Patients without liver metastases must have evidence of amplification or activating mutation of selected targets of cabozantinib (including MET, KIT, RET, VEGFR-1, VEGFR-2, VEGFR-3, FLT3, AXL, TRKB, or TIE2) by **at least one** of the following (See Section 4.4 for full detail):
  - a. DNA sequencing of metastatic tumor biopsy specimen or cfDNA test
  - b. RNA sequencing of metastatic tumor biopsy specimen
  - c. Commercial cell-free DNA assay
  - d. Overexpression by IHC on metastatic tumor biopsy specimen

12. Sexually active fertile subjects and their partners must agree to use medically accepted methods of contraception (*e.g.*, barrier methods, including male condom, female condom, or diaphragm with spermicidal gel) during the course of the study and for 4 months after the last dose of study treatment
13. Capable of understanding and complying with the protocol requirements and must have signed the informed consent document.

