#### 4.4 Molecular Eligibility

To be eligible, a patient's tumor must have evidence of gene amplification, an activating mutation, or overexpression of one of the following genes: MET, KIT, RET, VEGFR-1, VEGFR-2, VEGFR-3, FLT3, AXL, TRKB, or TIE2. In the event of activating mutations, the observed mutation must be of Level 1, Level 2, or Level 3 as annotated by OncoKB ([www.oncokb.org](http://www.oncokb.org)). Eligibility can be met by **at least one** of the following diagnostic tests:

- 1) DNA sequencing of a metastatic tumor biopsy specimen showing gene amplification or activating mutation using a CLIA-certified assay. Tumor tissue samples must have been collected within 6 months of enrollment.
- 2) Protein overexpression in a metastatic tumor biopsy specimen determined by immunohistochemistry (IHC) showing 3+ protein expression using a CLIA-certified assay. These

- include common in-house KIT and commercial reference labs for panTRK (*e.g.* NeoGenomics) and cMET (*e.g.* NeoGenomics, Caris, Mayo Clinic).
- 3) CLIA-certified commercial cell free DNA assay (either Guardant360 or FoundationOneLiquid assay) reporting gene amplification or activating mutation *within 6 months of enrollment*.
    - a. For the Guardant360 Liquid Biopsy amplification must be at least (++) or (+++) for to meet eligibility.
    - b. For the FoundationOneLiquid assay, amplification will be eligible. Reports that have an “equivocal” or “subclonal” designation will not be eligible.
  - 4) Any non-CLIA certified assay such as RNA expression profiling of a metastatic tumor biopsy specimen showing overexpression must be confirmed by a CLIA-certified assay (*i.e.*, immunohistochemistry showing 3+ protein expression)

Patients who do not meet molecular eligibility criteria will be allowed to enroll if they have liver metastases that meet RECIST criteria for measurable disease. Patients with prostate adenocarcinoma or NEPC will be allowed to enroll.

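### The tissue reference for tissue–plasma concordance is named as the inclusion test, which may be a plasma assay, IHC or no test at all

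*Combined protocol and SAP*

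**What the plan says.** Section 9.i says that the study will "compare tumor tissue targeted genomic sequencing results (CLIA test used for inclusion) with ctDNA findings at baseline and determine their concordance". The plasma side is the PCF SELECT panel, which Section 2.5 schedules at baseline, at 3 months and at progression. Section 9.i hopes that the results will support a blood-based entry test for later trials.

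Section 4.4 accepts any one of four molecular routes:

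- "DNA sequencing of a metastatic tumor biopsy specimen showing gene amplification or activating mutation using a CLIA-certified assay"
- "Protein overexpression in a metastatic tumor biopsy specimen determined by immunohistochemistry (IHC) showing 3+ protein expression using a CLIA-certified assay"
- "CLIA-certified commercial cell free DNA assay (either Guardant360 or FoundationOneLiquid assay) reporting gene amplification or activating mutation"
- a non-CLIA assay such as RNA profiling, which "must be confirmed by a CLIA-certified assay", with IHC 3+ given as the form of confirmation.

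Criterion 11 in Section 4.2 likewise accepts "DNA sequencing of metastatic tumor biopsy specimen or cfDNA test" and also lists IHC. It applies only to patients without liver metastases. Section 4.4 adds: "Patients who do not meet molecular eligibility criteria will be allowed to enroll if they have liver metastases", provided the lesions are measurable by RECIST. Section 12.1 plans up to 28 patients with liver metastases, and Section 12.2 sets the total at 30.

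On study sequencing of tissue, Section 12.4 lists whole exome and targeted DNA sequencing among the data to be generated. Section 9.iii describes DNA mutation analysis of the biopsy only as possible. Neither section links that sequencing to the concordance comparison. No section defines the evaluable pairs, the unit (patient or gene) or the agreement statistic.

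**The concern.** A concordance study of plasma against tissue needs a reference that is measured in tissue, at the DNA level, and obtained independently of the plasma result. The parenthesis in Section 9.i hands that role to whichever test admitted the patient, and only one of the four molecular routes meets the description. For the other patients the reference is of the wrong kind or does not exist.

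What is at stake is the use that Section 9.i has in mind. A figure meant to show how well plasma finds tissue alterations could instead reflect how patients happened to enter the trial.

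**Working it through.** The documents give no target, rate or sample size for concordance, so there is no figure to reproduce. The check sets the sections side by side.

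**What each entry route supplies as a reference**

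| Entry route (Sections 4.2 and 4.4) | Qualifying result | Tissue DNA sequencing? |
|---|---|---|
| Sequencing of a metastatic biopsy | Tissue DNA | Yes |
| IHC 3+ | Tissue protein | No |
| Commercial cfDNA assay | Plasma DNA | No |
| RNA profiling confirmed by IHC 3+ | Tissue RNA, then protein | No |
| Measurable liver metastases | None required | No |

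**Reading A: the parenthesis governs.** The reference is the inclusion test, whatever it was.

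- Men who qualified by cfDNA are compared plasma with plasma, after being selected for a positive plasma result. This pushes agreement up.
- Men who qualified by IHC are compared protein with DNA. This pushes agreement down to the extent that overexpression occurs without a DNA alteration.
- Men who entered on liver metastases alone have no reference.

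For direction only, let *t* be the true tissue–plasma agreement, *p* the plasma–plasma agreement and *s* the share of references that are really plasma. Then apparent agreement = (1 − *s*)*t* + *sp*. None of these values is in the documents. Assume *p* = 95%.

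| Assumed *t* | *s* = 25% | *s* = 50% |
|---|---|---|
| 60% | 0.75 × 0.60 + 0.25 × 0.95 = 68.75% | 0.50 × 0.60 + 0.50 × 0.95 = 77.5% |
| 80% | 0.75 × 0.80 + 0.25 × 0.95 = 83.75% | 0.50 × 0.80 + 0.50 × 0.95 = 87.5% |

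A share of IHC references would pull the other way, so even the net direction depends on the mix.

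**Reading B: the words about tumor tissue sequencing govern.** Men who qualified by cfDNA or IHC drop out, as do men who entered on liver metastases alone. Those who remain were admitted because their tissue result was positive, so for the qualifying alteration there are few negatives.

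The number of pairs is not given. If 28 of the 30 patients enter with liver metastases, only 30 − 28 = 2 are required to have any molecular inclusion test, and those two need not have used tissue sequencing. More pairs arise if patients with liver metastases also have a tissue report on file. Exact (Clopper–Pearson) 95% intervals show the precision, assuming 80% observed agreement except in the first row:

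| Agreeing / pairs | 95% interval |
|---|---|
| 2/2 | 16% to 100% |
| 8/10 | 44% to 98% |
| 16/20 | 56% to 94% |
| 24/30 | 61% to 92% |

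**Result.** The two readings analyse different patients and carry different faults. Nothing in Section 9 or Section 12.4 chooses between them.

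**The case against.** The strongest reply is that the sentence in Section 9.i has tumor tissue sequencing as its subject, and the parenthesis only says which sequencing report is meant. A plasma report is not tissue and IHC is not sequencing, so the plain reading would exclude both. This is a fair reading. A reader might infer that the plan, run as written, counts plasma-qualified men as concordant and IHC-qualified men as discordant, and the text does not establish that. But the plain reading leads to Reading B, where the analysis set is undefined, possibly very small and selected for positive tissue results.

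Three other inferences also go too far:

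- *Plasma-qualified men agree by construction.* The qualifying assay is a different product from PCF SELECT, and its report may date from up to 6 months before enrollment. Agreement is favoured but not guaranteed.
- *Negative agreement cannot be estimated at all.* PCF SELECT covers 74 target genes, and a man positive for one gene can be negative for others. Patients with liver metastases whose tissue was sequenced and found negative could also supply negatives. The shortage concerns the qualifying alteration, and only if the inclusion test remains the reference.
- *IHC 3+ means that there is no DNA change.* Overexpression does not rule out amplification.

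It is also true that concordance is not among the objectives in Section 1.2.3, has no hypothesis test in Section 12.4 and drives no trial decision. That limits the weight of the point but does not supply the missing reference.

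**Conclusion.** The point holds as a defect of definition in an exploratory analysis. The stated reference is of the wrong kind or absent for possibly most of the cohort. This follows from the text alone: criterion 11 and Section 4.4 admit patients on cfDNA or IHC, and up to 28 of 30 patients need no molecular test.

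No bias figure can be attached. The documents state neither the mix of entry routes nor any agreement rate, and the worked percentages show direction under assumed values only. The primary endpoint, the secondary endpoints and the sample size are unaffected. The correction is still worth making, because a better reference is already listed in Section 12.4 and baseline tumor genomics is needed anyway for the third exploratory objective in Section 1.2.3.

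**What to change.** Amend Sections 9.i and 12.4 as follows:

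1. Replace the parenthesis. The reference is DNA sequencing of baseline tumor tissue, either the CLIA tissue report or the whole exome or targeted sequencing listed in Section 12.4. It applies to every patient with such a result, whatever the entry route and including patients with liver metastases.
2. State that a cfDNA or IHC report is never used as the tissue reference.
3. Report positive and negative agreement by gene, over the genes covered by both assays, with exact intervals and the number of pairs.
4. Report these separately for men who did and did not qualify by cfDNA.
5. Classify men who qualified by IHC or RNA according to their tissue DNA result. Excluding them would bring back the dependence on entry route.

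The cost is wording only, so long as the analysis is limited to patients whose baseline tissue is actually sequenced. The small downside is that Section 9.iii leaves biopsy DNA analysis optional. The number of evaluable pairs is therefore uncertain and should be reported with the result. Requiring sequencing in every patient could add assays, and this fix does not ask for it.
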